8.2 Overall Study Design

The overall study design is illustrated in [Figure 1](#) (Part 1) and [Figure 2](#) (Part 2).

For Parts 1 and 2, screening for eligibility will occur from Days -2 to -1. After screening, subjects will undergo the baseline visit, which is also Day 0.

Subjects will complete study visits either as inpatient or outpatient visits, in accordance with institutional practice. Following the first 2 weeks of every other day study treatment (GLASSIA in Part 1; GLASSIA or control in Part 2), subjects will undergo visits on the following days to have study treatment administered (through Day 49) and to perform safety follow-up and study procedures: Days 14, 21, 28, 35, 42, 49 and 56.

All subjects will be treated with study treatment in combination with conventional steroid treatment through Day 49, or until treatment failure, withdrawal from treatment or withdrawal from the study, whichever comes first. Thereafter, subjects will be treated with standard-of-care for the remainder of their participation in the study based on the investigator's discretion. Subjects who are withdrawn from study treatment will continue to be followed through at least Day 28 (refer to Section 10.6), unless the subject withdraws consent.

Steroid treatment after Day 49 will be at the investigator's discretion. Subjects will visit the site for follow-up visits on Days 56, 100, 180 and 365. In the event that it is not feasible for the subject to visit the site at Day 365, the visit may be conducted with a phone call.

Subjects will also receive standard antibiotic, antifungal and antiviral prophylactic treatment through Day 180 or per institutional guidelines.

Assessments of vital signs, clinical laboratory data (hematology and chemistry), local tolerability and AEs will be performed throughout the study.

Steroid Taper

Tapering of steroids may commence after a subject responds to therapy (overall response, also referred to as GvHD response, as defined in Section 8.4.1); however, the dose of steroid should not be tapered below 2 mg/kg/day (methylprednisolone or equivalent dose) before Day 2 or below 0.25 mg/kg/day (methylprednisolone or equivalent dose) before Day 28.

Subjects who discontinue study treatment (GLASSIA or control) will be treated with standard-of-care for the remainder of their participation in the study.

Treatment Failures

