Prior to Day 28 in Parts 1 and 2, subjects must be withdrawn from study treatment if a second-line treatment for acute GvHD is introduced. Second-line treatment may be introduced per investigator discretion prior to Day 28 if a subject experiences disease progression and/or new organ involvement or no change in acute GvHD status after at least 7 days of study treatment (Day 6). Subjects who experience recurrent malignancy will also be withdrawn from study treatment (Section 12.11).

An increase in steroid dose following steroid taper does not constitute second-line treatment; however, steroid treatment at methylprednisolone doses (or equivalent) of greater than 2 mg/kg/day for GvHD treatment will be considered a treatment failure.

Subjects classified as treatment failures will be included in the analysis, but will not be counted as either CR or PR for the primary (overall response) or key secondary (GI response) endpoints. Subjects classified as treatment failures will not be replaced.

All subjects will be followed up at Days 100, 180 and 365.

Data Monitoring Committee

A Data Monitoring Committee (DMC) will independently evaluate safety and efficacy data (Section 15.4). The recommendations of the DMC will be based on the analysis of safety in Parts 1 and 2 and the interim analysis of Part 2 (Section 8.2.2).

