10.6 Subject Completion/Discontinuation

A subject is considered to have completed the study when he/she ceases active participation in the study according with the protocol (with or without protocol deviations).

Reasons for completion/discontinuation will be reported on the Completion/Discontinuation CRF, including: completed, screen failure, AE (eg, death), discontinuation by subject (eg, lost to follow-up [defined as 3 documented unsuccessful attempts to contact the subject], dropout), physician decision (eg, pregnancy, progressive disease, non-compliance with IP/protocol violation(s), recovery), study terminated by sponsor, or other (reason to be specified by the investigator, eg, technical problems). Regardless of the reason, all data available for the subject up to the time of completion/discontinuation through the study follow-up period should be recorded on the appropriate CRF.

Every effort will be made to have discontinued subjects complete the study completion/termination visit. If the study completion/termination visit is done as an additional, unscheduled visit, the assessment results shall be recorded with the study completion/termination visit. If a subject terminates participation in the study and does not return for the study completion/termination visit, their last recorded assessments shall remain recorded with their last visit. The reason for discontinuation will be recorded, and the data collected up to the time of discontinuation will be used in the analysis and included in the clinical study report. If additional assessments are required, the assessments shall be recorded separately. Assessments to be performed at the study completion/termination visit (including in cases of withdraw or discontinuation) can be found in Supplement 20.2 Schedule of Study Procedures and Assessments.

Subjects who discontinue study treatment prior to Day 28 will complete the Day 28 visit on Day 28 (± 1 day). If at least 2 weeks have passed since the last dose of study treatment, the Day 28 visit will serve as the study completion/termination visit. If Day 28 is less than 2 weeks following the last dose of study treatment, subjects will complete the Day 28 visit and then the study completion/termination visit 2 weeks (± 1 day) after the last dose of study treatment. In this event, the study completion/termination visit will consist of an office visit with the same assessments as the Day 365 visit.

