Subjects who discontinue study treatment after Day 28 will complete the study completion/termination visit as an office visit 2 weeks (± 1 day) after the last dose of study treatment. Subjects who withdraw from the study after Day 56 will be encouraged to complete the study completion/termination visit at the time of discontinuation. In the event that it is not feasible for the subject to visit the site at the study completion/termination visit after Day 56, the visit may be conducted with a phone call.

Subjects who discontinue study treatment will not attend any other subsequent visits other than Day 28 and the study completion/termination visit (if applicable), except as needed for follow-up of recovering/resolving AEs (see Section 12.1.2).

In the event of subject discontinuation due to an AE, clinical and/or laboratory investigations that are beyond the scope of the required study observations/assessments may be performed as part of the evaluation of the event. These investigations will take place under the direction of the investigator in consultation with the sponsor, and the details of the outcome may be reported to the appropriate regulatory authorities by the sponsor.

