11.12 Mortality and Survival Assessments

All-cause, transplant-related, infection-related and GvHD-related mortality will be calculated as the time from HSCT to death; the cause of death will be based on the investigator's assessment. The date and cause of death, if applicable, will be collected in the eCRF at the visits indicated in Table 1. The following definitions will be used by the investigator to assess the cause of death. These categories are not mutually exclusive, and the investigator will select all applicable categories:

- Transplant-related mortality: death related to transplantation (including deaths related to GvHD)
- Infection-related mortality: death related to infection (including infections related to HSCT)
- GvHD-related mortality: death related to GvHD
- Other cause: any death not related to transplant, infection or GvHD

Failure-free survival, GvHD-free survival and overall survival will be collected in the eCRF at the visits indicated in Table 1.

Failure-free survival is determined by the investigator and defined as the absence of all 3 of the following criteria:

- Need for second-line treatment for acute GvHD
Second-line treatment is defined as any additional systemic treatment used for steroid nonresponsive treatment of acute GvHD. Methylprednisolone (or equivalent steroid) doses greater than 2 mg/kg/day required for the treatment of GvHD will also be considered second-line therapy

- Non-relapse mortality
Non-relapse mortality is defined as death during continuous complete remission
- Recurrent malignancy

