12.1.2 Assessment of Adverse Events

For the purposes of this study, changes in the severity or duration of GvHD experienced after the first IP exposure are collected as an efficacy endpoint and thus are not reportable on the AE CRF, nor will they be included in the analysis of AEs.

Symptoms or diagnostic findings of GvHD, such as skin rashes, abnormal liver function tests, diarrhea, ileus and bowel perforation, should be collected on the AE CRF only if there is an increase in the severity, duration or frequency AND if they begin after first exposure to IP.

All other AEs from the first IP exposure until study completion will be described on the AE CRF using the medical diagnosis (preferred), or, if no diagnosis could be established at the time of reporting the AE, a symptom or sign, in standard medical terminology in order to avoid the use of vague, ambiguous, or colloquial expressions (see definition in Section 12.1). Each AE will be evaluated by the investigator for:

- Seriousness as defined in Section 12.1.1.1
- Severity as defined in Section 12.1.2.1
- Causal relationship to IP exposure or study procedure as defined in Section 12.1.2.2

For each AE, the outcome (ie, recovering/resolving, recovered/resolved, recovered/resolved with sequelae, not recovered/not resolved, fatal, unknown) and if applicable action taken (ie, dose increased, dose not changed, dose reduced, drug interrupted, drug withdrawn, not applicable or unknown) will also be recorded on the AE CRF. Recovering/resolving AEs will be followed until resolution or 30 days after the study completion/termination visit, whichever comes first. The follow-up information will be documented in the AE CRF. If the severity rating for an ongoing AE changes before the event resolves, the original AE report will be revised (ie, the event will not be reported as separate AE). During the course of any AE, the highest severity rating will be reported.

Deviations from protocol-specified procedures of IMP use such as overdosing, underdosing, withdrawal, omission, incorrect route of administration, and use of a product other than the IMP, standard care of the underlying disease or treatment of a TEAE shall be recorded in the Protocol Deviation Form.

Any pregnancy that occurs after administration of IP will be reported on a Pregnancy Report Form.

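### Sections 8.2 and 10.6 disagree on follow-up after study treatment stops; if 10.6 is followed and later deaths are not learned of, survival in each arm is likely to be overstated

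*Protocol*

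**What the plan says.** **Follow-up continues.** Protocol Section 8.2, under Treatment Failures, states: "All subjects will be followed up at Days 100, 180 and 365". The same section says that subjects who stop study treatment receive standard of care for the rest of their participation, which implies that participation goes on.

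**Follow-up ends.** Section 8.2 also sets a floor and refers elsewhere: "Subjects who are withdrawn from study treatment will continue to be followed through at least Day 28 (refer to Section 10.6"). Section 10.6 then says: "Subjects who discontinue study treatment will not attend any other subsequent visits other than Day 28 and the study completion/termination visit (if applicable"). Footnote a of Tables 1 and 2 repeats this. For a stop before Day 28 with at least two weeks since the last dose, "the Day 28 visit will serve as the study completion/termination visit". Otherwise the termination visit comes two weeks after the last dose. The one exception reads "except as needed for follow-up of recovering/resolving AEs", and Section 12.1.2 limits it: "Recovering/resolving AEs will be followed until resolution or 30 days after the study completion/termination visit, whichever comes first". Section 9.3 gives subjects who leave the study the same horizon, Day 28 or two weeks after the last dose.

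**Data collection and analysis.** Section 11.12 states: "The date and cause of death, if applicable, will be collected in the eCRF at the visits indicated in Table 1". Section 10.6 adds that "the data collected up to the time of discontinuation will be used in the analysis and included in the clinical study report". Section 13.4.2 plans Cox and Kaplan-Meier analyses of overall survival in Part 2 and gives no censoring rule. SAP Section 7.2.2, for Part 1 only, censors at study completion or early termination, or at the last recorded date. That SAP follows the original protocol and marks these analyses as not applicable.

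**The concern.** Section 8.2 requires study treatment to stop when second-line treatment starts before Day 28. Both follow-up rules therefore apply to the same subjects, and a site cannot tell which one governs.

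These subjects are unlikely to be typical of those still followed. Section 6.2 puts one-year survival after steroid non-response at 5% to 30%. If they leave survival follow-up at Day 28 to 56, the Kaplan-Meier estimate treats them as having the later hazard of those who remain, and survival in each arm comes out too high.

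The outcomes exposed are:
- overall survival at Days 100, 180 and 365;
- later all-cause and cause-specific mortality;
- collection of chronic GvHD from Day 100 and of late infections;
- possibly GvHD-free survival at Days 100 and 180, in stoppers who have not yet had an event.

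Which mortality landmarks are affected depends on the time origin. This is HSCT in protocol Sections 11.12 and 13.4.2, and first dose in SAP Section 7.2.2.

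**Working it through.** **1. Last scheduled visit under Section 10.6.** This is the later of Day 28 and last dose + 14 days (each ±1 day). The adverse event exception adds at most 30 days.

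| Last dose | Last visit | With full AE window |
|---|---|---|
| Day 14 or earlier | Day 28 | Day 58 |
| Day 21 | Day 35 | Day 65 |
| Day 28 | Day 42 | Day 72 |
| Day 35 | Day 49 | Day 79 |
| Day 42 | Day 56 | Day 86 |

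No row reaches Day 100. Between 365 − 56 = 309 and 365 − 28 = 337 days have no scheduled visit.

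**2. Size of the effect.** The plan gives no figure to reproduce, so this is an illustration timed from Day 0.

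From the protocol: Day 28 response of 40% in control and 65% with GLASSIA (Section 13.1), and 74 subjects per arm.

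Assumed:
- Exponential survival, with Day 180 survival of 85% in responders and 50% in non-responders. The latter gives 0.5^(365/180) = 24.5% at one year, inside the protocol's 5% to 30%. The responder figure is not in the documents.
- A share f of non-responders stops, uniformly over Days 6 to 27. Of these, 15/22 exit on Day 28 and 7/22 on Day 35. The share is not in the documents, so it is varied.
- All others are followed throughout.

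Let R(t) = 0.85^(t/180), N(t) = 0.5^(t/180), p = response rate, and M_w(t) = p·R(t) + (1 − p)·w·N(t).

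True Day 180 survival:
- control: 0.40 × 0.85 + 0.60 × 0.50 = 64.0%
- GLASSIA: 0.65 × 0.85 + 0.35 × 0.50 = 72.75%
- difference: 8.75 points

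Expected Kaplan-Meier value = M_1(28) × [M_a(35)/M_a(28)] × [M_b(180)/M_b(35)], with a = 1 − f × 15/22 and b = 1 − f.

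At f = 50%:
- control: 0.9287 × (0.7331/0.7450) × (0.4900/0.6497) = 0.689, overstated by 4.9 points
- GLASSIA: 0.9480 × (0.8314/0.8409) × (0.6400/0.7827) = 0.766, overstated by 3.9 points

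| f in both arms | Control overstated | GLASSIA overstated | Difference (true 8.75) |
|---|---|---|---|
| 30% | 2.5 | 2.2 | 8.4 |
| 50% | 4.9 | 3.9 | 7.7 |
| 80% | 10.4 | 7.0 | 5.4 |

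If every stopper had the full 30-day adverse event window, the overstatement at 30% and 50% stopping would be 2.0 and 3.9 points in control and 1.7 and 3.0 with GLASSIA.

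**3. Against sampling error.** SE of the difference = √(0.64 × 0.36/74 + 0.7275 × 0.2725/74) = 7.6 points. The shift of 0.4 to 1.0 point at 30% to 50% stopping is small beside it.

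**4. Sensitivity.**
- Unequal stopping: with 30% in control and 50% with GLASSIA the difference rises to 10.1 points. With the shares reversed it falls to 6.0.
- Non-responder survival at the ends of the protocol's range (0.05^(180/365) = 22.8% and 0.30^(180/365) = 55.2% at Day 180): control at 50% stopping is overstated by 8.5 and 4.2 points.
- Stopping unrelated to prognosis gives no bias.

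**5. Deaths not seen.** At 50% stopping, 0.5 × 0.6 × 74 = 22.2 control subjects stop. The share alive at exit is 15/22 × 0.898 + 7/22 × 0.874 = 0.890, or 19.8 subjects. By Day 180, 11.1 of the 22.2 are alive. So 19.8 − 11.1 = 8.7 of 74 × 0.36 = 26.6 expected control deaths fall after exit.

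Stops after Day 28 and stops by responders are not modelled.

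**The case against.** A reader might infer that treatment failures will certainly be lost to survival follow-up. The documents do not support that. Section 10.6 restricts visits attended, so telephone or chart follow-up could satisfy both sections. It also asks for available data to be recorded through the study follow-up period. Section 8.2 sets Day 28 only as a minimum and describes participation as continuing. The SAP censors subjects not known to have died, so a death learned of later could count. Applying that Part 1 rule to Part 2 is itself an assumption. Early censoring is therefore one reading. What remains is that no contact after the termination visit is described, and nothing requires later deaths to be sought.

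A reader might also infer that the treatment comparison is materially biased in a known direction. It is not shown to be. At 30% to 50% stopping, equal in both arms, the shift is well inside sampling error, and it can go either way when the stopping shares differ.

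Nor should the Section 8.2 sentence be dismissed as left over from the deleted retreatment option. SAP Section 2 does carry it with a retreatment clause. In the current protocol it stands under Treatment Failures without that clause, and can equally be deliberate.

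Some outcomes are untouched or little affected. The Day 28 visit is kept for stoppers, so the primary and key secondary endpoints stand. Failure-free survival is largely unaffected in treatment failures, because second-line treatment and recurrent malignancy are themselves events.

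**Conclusion.** The contradiction is in current protocol text and should be fixed. Its consequence is conditional: if Section 10.6 is followed and deaths are not otherwise learned of, subjects with a likely higher death hazard leave survival follow-up by about Day 56, or by about Day 86 with the adverse event exception.

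The main effect would be on survival levels within each arm: under the stated assumptions, about 2.5 to 4.9 points in control and 2.2 to 3.9 with GLASSIA at Day 180, for 30% to 50% of non-responders stopping before Day 28. These figures rest on an assumed responder survival, exponential hazards, an assumed stopping share and a Day 0 origin. The mortality landmarks would shift if timed from HSCT.

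Only other secondary and safety outcomes are exposed. SAP Section 1 records that the study ended with one subject enrolled and that only listings are produced. This is therefore a defect of the plan, not of any reported result.

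**What to change.** Reconcile Section 10.6 and footnote a of Tables 1 and 2 with Section 8.2, so that stopping study treatment does not end study participation. Unless consent is withdrawn, collect vital status and date and cause of death at Days 100, 180 and 365, by telephone or chart review where needed. State for Part 2 that overall survival is censored at the date last known alive, and use one time origin for mortality in the protocol and the SAP.

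The cost is protocol wording plus up to three contacts per discontinued subject. Non-responders number 0.60 × 74 + 0.35 × 74 = 70.3. At 50% stopping, 35.2 stop and 35.2 × 0.890 = 31.3 are alive at exit, which gives about 94 contacts. At 80% stopping the same method gives about 150. Responders who stop and stops after Day 28 would add to either figure. Section 8.2 already allows a telephone visit at Day 365.

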10.7 Procedures for Monitoring Subject Compliance

All study procedures are to be performed under the direct supervision of the investigator/a licensed healthcare professional at the study site, and thus, no separate procedures will be used to monitor subject compliance.

11. ASSESSMENT OF EFFICACY AND PHARMACOKINETICS

11.1 Demographics and Baseline Characteristics

At screening, the following subject demographics will be collected:

- Gender
- Date of birth
- Race and ethnicity (where permitted by local regulations)
- Smoking status

At screening, the following subject baseline characteristics will be collected: medical, surgical and transplant history, including the date and source of HSCT.

11.2 CMV and HIV Testing

At screening and at the visits indicated in [Table 1](#), subjects will be tested for CMV, using antigenemia or polymerase chain reaction–based assays according to institutional guidelines. Subjects with evidence of CMV viremia (based on either assay) will receive antiviral therapy based on the investigator’s standard practice. Subjects may be tested for CMV at additional visits not indicated in [Table 1](#), per institutional guidelines.

At screening, subjects will be tested for HIV using the antibody or nucleic acid test. If HIV testing was performed within the 3 months prior to screening, the results of the earlier tests may be used instead.

11.3 Lower GI Biopsy

Subjects will have a lower GI biopsy within 7 days of informed consent. If a biopsy was performed within 3 days prior to screening, results from that biopsy may be used instead. The type of lower GI biopsy is at the investigator’s discretion based on their standard institutional practice. If in the opinion of a pathologist, the results of the lower GI biopsy are inconsistent with acute GvHD, the subject will be withdrawn from the study. Results of the biopsy will not be required to assess eligibility prior to the first dose of study treatment, but are required for continuation in the study.

11.4 GvHD Staging/Assessment

At screening and at the visits indicated in [Table 1](#), GvHD will be assessed for severity. Grading of GvHD will be performed by the investigator according to the modified IBMTR grading system¹⁵, which classifies the degree of involvement of each organ system by stage on a scale of 0 to 4 and the grade of severity of acute GvHD on a scale of A to D. The IBMTR grading system is modified on the basis of UpToDate¹⁵ and is summarized below.

The degree of **skin involvement** is staged depending upon the degree and severity of the lesions as follows:

- Stage 1: Maculopapular rash over <25% of body area
- Stage 2: Maculopapular rash over 25 to 50% of body area
- Stage 3: Generalized erythroderma
- Stage 4: Generalized erythroderma with bullous formation, often with desquamation

The degree of **GI involvement** is staged based upon the severity of diarrhea as follows:

- Stage 1: Diarrhea 500 to 1000 mL/day
- Stage 2: Diarrhea 1000 to 1500 mL/day
- Stage 3: Diarrhea 1500 to 2000 mL/day
- Stage 4: Diarrhea >2000 mL/day OR pain OR ileus

The degree of **liver involvement** is staged based upon the serum total bilirubin level as follows:

- Stage 1: Bilirubin 2 to 3 mg/dL
- Stage 2: Bilirubin 3 to 6 mg/dL
- Stage 3: Bilirubin 6 to 15 mg/dL
- Stage 4: Bilirubin >15 mg/dL

The modified IBMTR grading system defines the severity of acute GVHD as follows:

- Grade A: Stage 1 skin involvement alone (maculopapular rash over <25% of the body) with no liver or gastrointestinal involvement
- Grade B: Stage 2 skin involvement and/or Stage 1 to 2 gut or liver involvement
- Grade C: Stage 3 involvement of any organ system (generalized erythroderma; bilirubin 6.1 to 15.0 mg/dL; diarrhea 1500 to 2000 mL/day)
- Grade D: Stage 4 involvement of any organ system (generalized erythroderma with bullous formation; bilirubin >15 mg/dL; diarrhea >2000 mL/day OR pain OR ileus)

The investigator will record the grade of GvHD (A through D) and the stage for each organ system (0 to 4) in the eCRF.

